Randomization will be used in the study to allot one of the two treatment methods used for canine retraction to each side of the mouth to minimize bias and to account for individual variability. By randomly assigning different retraction methods to each side of the mouth any individual-specific factors that may affect the treatment outcomes (oral hygiene habits, masticatory habits) are likely to be equally distributed across the treatment group. Block randomization will be performed to code the type of retraction method in this trial and to determine the sequence of its administration to each participant. This will be controlled by a research faculty member of the Section of Dentistry at AKUH.

Sequence Generation:

In this two-armed study, four-blocks, each with a block size of six-possible allocation sequences for treatment arms will be generated.

(1) AABB, (2) BBAA, (3) ABAB, (4) BABA, (5) ABBA, (6) BAAB

The blocks to be utilized and their order will be determined by the research faculty member using sealed envelopeTM online software.²⁴

Allocation Sequence Concealment:

After fulfilling the inclusion criteria and obtaining consent, the patient will be recruited in the study. During the recruitment of the participants in the trial, the sealed envelope for a participant will be opened by the enrolling team member and will be allotted an intervention according to the ascending order sequence already generated by the principal investigator who is also a biostatistician.

Enrollment:

After obtaining approval from the ERC (AKUH), each participant fulfilling the inclusion criteria for the study and consenting to participate in the trial will be assigned a participant ID.

Blinding:

The study investigators, patients recruited, and assessors will not be blinded during the trial. All the measurements will be recorded by the co-investigator on the study proforma (Annexure H).

POSSIBLE RISKS OR BENEFITS:

Nickel is a known allergen, though people with nickel allergy tolerate stainless steel brackets and wires quite satisfactorily.²⁵ However, in case of any adverse events such as allergic reaction to Ni-Ti closed-coil spring such as contact dermatitis, rash, bumps, redness or irritation of the skin or mucosa, its use will be stopped, and patient will be excluded from the study.

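### The protocol names two generators of the allocation sequence and lists only blocks of four in an open-label trial, so about a third of side assignments can be deduced in advance

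*Protocol*

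**What the plan says.** On who makes the list, the protocol gives two accounts:

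- Randomization: "This will be controlled by a research faculty member of the Section of Dentistry at AKUH".
- Sequence Generation: "The blocks to be utilized and their order will be determined by the research faculty member", using online software.
- Allocation Sequence Concealment: allocation follows the "ascending order sequence already generated by the principal investigator who is also a biostatistician".

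On the blocks, Sequence Generation states: "In this two-armed study, four-blocks, each with a block size of six-possible allocation sequences for treatment arms will be generated". The list that follows is "1) AABB, (2) BBAA, (3) ABAB, (4) BABA, (5) ABBA, (6) BAAB". No other block length appears, and the letters A and B are not defined.

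On concealment, "the sealed envelope for a participant will be opened by the enrolling team member", once eligibility and consent are settled. On blinding, "The study investigators, patients recruited, and assessors will not be blinded during the trial". The co-investigator screens patients (Study Groups) and records all measurements (Blinding).

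The thing randomised is the side: in each patient, one device goes to the right quadrants and the other to the left (Operational Definitions, Data Collection Procedure). The planned number is 46 (Sample Size).

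**The concern.** Two separate matters bear on whether the coming assignment is hidden from those who recruit.

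First, the generator knows every assignment. The protocol attributes that role both to a research faculty member and to the principal investigator. For neither does it say that the person stays out of enrolment, treatment or measurement.

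Second, short blocks of one fixed length, printed in the protocol, let an observer work out later assignments from earlier ones. In an open-label trial every earlier assignment is visible in the mouth. The co-investigator role both screens and measures, so the person judging eligibility is also placed to see the history.

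At stake is the fairness of the left/right assignment. Someone who expected one canine to move more readily, and knew which side would receive the spring next, could enrol the patient now, later or not at all. That would tilt the within-patient comparison on which the trial rests.

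**Working it through.** **1. Who generates the list.** Set side by side, two sections give the decision on blocks and order to the research faculty member, and a third says the principal investigator had already generated the sequence. Nothing identifies the two as one person. The text does not show which account is intended.

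**2. Block length.** With equal allocation, a block of length four has C(4,2) = 6 balanced orders. These are exactly the six listed, so the list implies a length of four. The sentence introducing it does not fit if taken literally:

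- Four blocks of four cover 4 × 4 = 16 participants.
- Four blocks of six cover 4 × 6 = 24, and a block of six would have C(6,3) = 20 orders, none of length four.
- The planned 46 participants need 46 / 4 = 11.5, so 12 blocks of four.

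The kindest reading is blocks of length four, each drawn from six possible orders.

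**3. Across participants or within a mouth?** Each patient has four quadrants, so four letters could in principle denote quadrants. One envelope per participant and a sequence used in ascending order point instead to one letter per participant. The figures below take that reading, with each letter standing for one right/left arrangement (an assumption, since the letters are undefined).

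**4. Predictability.** Assume the observer knows the length is four, knows where blocks start and has seen all earlier allocations. An assignment is certain when one letter is used up within its block.

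| Position in block | Probability it is certain | Probability best guess is right |
|---|---|---|
| 1 | 0 | 1/2 |
| 2 | 0 | 2/3 |
| 3 | 2/6 (AABB, BBAA) | 1/3 × 1 + 2/3 × 1/2 = 2/3 |
| 4 | 1 | 1 |

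- Certain per block: 1/3 + 1 = 1.33 of 4, or 33.3%.
- Best guess right per block: (0.5 + 0.667 + 0.667 + 1) / 4 = 2.833 / 4 = 70.8%.
- Over 46 participants there are 11 full blocks and 2 further places, neither of which is certain: 11 × 1.333 = 14.7 certain, or 14.7 / 46 = 32%.
- Best guess right over 46: (11 × 2.833 + 0.5 + 0.667) / 46 = 32.3 / 46 = 70.3%.

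With simple randomisation of side, no assignment is certain and the best guess is right 50% of the time. The person who generated the list knows 100% under any scheme.

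**5. Alternatives.** These block sizes are assumptions for illustration, with the observer knowing the set of sizes but not their order. In simulation (4,000 replicates of 46 participants), lengths 4 and 6 at random leave 5.7% of assignments certain and a best guess right 68.8% of the time. Lengths 4, 6 and 8 leave 2.4% and 67.8%. Varying the size removes most of the certainty but little of the guessing advantage while the observer knows the set of sizes.

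**The case against.** Several points on the other side are fair.

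- **The principal investigator is not said to recruit.** The co-investigator screens and an enrolling team member opens the envelope. Someone must hold the list, and a biostatistician generating it is no fault in itself. Nor does being unblinded break concealment, which is a separate matter. The two roles might also be one person. This stands: foreknowledge at recruitment through the list-holder is possible, not shown. The conflict in the text remains.
- **There are safeguards.** The envelope is opened only after consent, and sampling is consecutive, which leaves little formal room to defer or skip a patient. Both narrow the route to bias. Neither stops deduction, because a forced assignment is known before its envelope is opened.
- **The letters might mean quadrants.** If so, prediction between patients does not arise. This is the less likely reading, but the garbled sentence does not exclude it.
- **Blocking has a purpose.** A reader might infer that it is pointless because every patient receives both devices. That goes too far. Arm sizes are equal by design, but blocking also balances which side receives the spring, including at the interim look at half the sample. The benefit is small, not nil.
- **The bias mechanism is conjecture.** Nothing in the protocol shows that staff can tell which canine will move faster, and no patient can be steered to one device. This stands as a limit on size.

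**Conclusion.** The concern holds in a limited form. The protocol gives two unreconciled accounts of who generates the sequence, and its block sentence does not agree with its own list. On the likelier reading, fixed blocks of four across participants, an observer of past allocations is certain of about 15 of 46 side assignments and guesses right about 71% of the time (70.8% per full block, 70.3% over 46).

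A reader might infer that the next side is generally known before enrolment, or that the principal investigator can steer allocation. The document supports neither: about two thirds of assignments remain uncertain to an observer, and no recruiting role is given to the principal investigator.

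Because every patient receives both devices, the only route to bias is the choice or timing of enrolment given the coming side. Its size cannot be computed from the protocol and is probably modest. The point does not undermine the design, but should be corrected because the remedy is cheap. The figures assume that the observer knows the block length, the block starts and all earlier allocations.

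**What to change.** - Reconcile the two statements: name one generator and list-holder, and state that this person takes no part in enrolment, treatment or measurement. The document gives no basis for choosing between the two roles, so the sponsor must decide and confirm that the condition is met.
- Correct the block sentence so that block length, number of blocks and the 46 participants agree, and define what A and B stand for.
- Replace fixed blocks of four with simple randomisation of side for each patient. This removes prediction from past allocations altogether. If right/left balance is wanted, use randomly varying block sizes that are not disclosed to enrolling staff. This removes most of the certainty but leaves some advantage to a guesser.

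The cost is a few sentences and one setting in the randomisation software. Simple randomisation may leave an uneven right/left split. With 46 patients the number with the spring on the right has mean 23 and standard deviation √(46 × 0.25) = 3.4, so about 16 to 30 in 95% of trials (23 ± 1.96 × 3.4). This should matter little for a within-patient comparison.

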Elastomeric power chains are resilient and latex-free orthodontic materials. They are made up of elastic material and consist of many connected rings. Each ring is engaged in a bracket to apply a force of 175-300 gm.

Plaque Index:¹⁷ (Annexure C)

Plaque index is a grading system used to assess the amount of plaque present at the gingival margins and helps in assessing oral health. It consists of four grades including, Grade 0, 1, 2 and 3. The increase in grade indicates the increased amount of plaque along the gingiva.

Gingival Index:²¹ (Annexure D)

Gingival index is a grading system that is used to assess the health of the gingiva. It consists of four grades including, Grade 0, 1, 2 and 3. The increase in grade indicates the compromised gingival health of the teeth.

Root Resorption:²²

Root resorption is a decrease in root length and width due to an inflammatory process. In orthodontics, during tooth movement, areas of necrosis develop called hyalinized areas, which result in root resorption. Periapical radiographs will be taken to assess the amount of root resorption by determining the length of the tooth from the cusp tip to the root apex.

Retraction Rate:¹⁶

The retraction rate of canine will be the distance travelled divided by the time interval needed for closure of spaces. It will be noted at four-time intervals i.e at the start of the canine retraction (T_0), after first month (T_1), second month (T_2) and third month follow-up (T_3).

Split-mouth Study:

A randomized controlled trial in which intervention and control are randomly allocated to the different quadrants in the oral cavity. In our study, Ni-Ti closed-coil springs and elastomeric power chains will be randomly allocated to the right and left quadrants of maxillary and mandibular arches.

MATERIAL & METHODS:

Study Design: A single center open labelled parallel split-mouth randomized controlled trialSettings: Dental clinics, Department of Surgery, The Aga Khan University Hospital, Karachi, Pakistan

Study Duration: One year after ethical review committee (ERC) approval **Sampling Technique:** Non-probability consecutive sampling

SAMPLE SIZE:

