After obtaining an approval from the Ethical Review Committee and taking informed consent and informed assent from the parents and child respectively, (Annexure E, F and G), these patients will be recruited in the study as participants. Patients visiting the orthodontic clinic at the Aga Khan University Hospital Karachi will be included in this study. Detailed information regarding the study will be provided to the participants and they will be given the choice to either accept or refuse their inclusion in the study. After the extraction of all first premolars under local anesthesia, 0.018" stainless steel archwires will be inserted in the maxillary and mandibular arches. For canine retraction, Ni-Ti closed-coil springs and elastomeric power chains will be randomly allocated to the right and left quadrants of both arches. Radiographic measurement (root resorption) and clinical measurements (canine retraction, plaque accumulation and gingival health) will be

recorded at four points in time. First, at the start of the canine retraction (T_0), after first month (T_1), second month (T_2) and third month follow-up (T_3). Canine retraction rate will be recorded by using a 100 mm marked scale.¹⁶ Data will be collected on an organized study proforma (Annexure H).

Ethical Considerations:

This study will be carried out as per the guidelines of the World Medical Association's Declaration of Helsinki.²³ and the principles of Good Clinical Practice (GCP). Any modifications in the protocol will be re-submitted to the ERC. The study will be conducted in compliance with regulations and a copy of the final study protocol will be submitted to ERC. All the recorded data of patients will remain confidential. Access will be provided to no one except the investigators. Participants' names and identities will remain undisclosed; however, data may be seen by ERC or any local regulatory body. Data will be saved for 7 years as per GCP and institutional guidelines.

Randomization:

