Adverse events will be reported to ERC within a week and any serious adverse event will be reported to the Department of surgery, sponsors, CTU, DRC, and ERC within 24 hours. All emergency side effects will be managed in the emergency department and the Department of Surgery will bear the charges.

STUDY GROUPS:

The patients will be screened using the inclusion and exclusion criteria by the co-investigator. Measurements for the canine root resorption, retraction rate, plaque accumulation and gingival health will be taken at T_0 , T_1 , T_2 and T_3 .

Intervention: Ni-Ti closed-coil springs **Control:** Elastomeric power chains

The participants will receive routine instructions for oral hygiene maintenance and care of the appliance verbally.

MATERIAL STORAGE:

Ni-ti closed-coil springs and Elastomeric power chains will be stored at room temperature at the Department of Surgery, Dental inventory.

DATA ANALYSIS:

Data will be entered and analyzed in SPSS for Windows (version 23.0, SPSS Inc. Chicago). Frequencies and proportions will be reported for categorical variables, such as gender. Shapiro-Wilk test will be used to check the normality of the data. Descriptive statistics, such as means and standard deviations for normally distributed or median and interquartile range (IQR) for non-normally distributed data will be reported for all baseline clinical factors. Paired t-test will be used for the pairwise comparison. For the two groups the mean/median scores for retraction rate, root resorption, gingival health and plague accumulation between the two groups will be assessed using Independent t-test for normally distributed data and Man-Whitney U test for non-normally distributed data. A *p*-value ≤ 0.05 at 95% confidence interval will be considered as statistically significant.

On achieving 50% of the sample size, an interim analysis will be run, if the results show that the given intervention is successful in significantly improving the rate of canine retraction in patients then further trial will be stopped and all the participants will be given the intervention.

FINANCE:

Departmental funds from the Department of Surgery and intramural grants will be applied for.

PUBLISHING POLICY/PLAN:

For publication the data will be utilized, and it could be presented in either national or worldwide forums.

DATA CONFIDENTIALITY:

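### Root resorption films are to be read unmasked, although stored films can be coded and read without device or visit label

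*Protocol*

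**What the plan says.** Protocol, Blinding: "The study investigators, patients recruited, and assessors will not be blinded during the trial". The next sentence adds "All the measurements will be recorded by the co-investigator on the study proforma (Annexure H").

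Protocol, Operational Definitions, in the entry for root resorption, gives the method: "Periapical radiographs will be taken to assess the amount of root resorption by determining the length of the tooth from the cusp tip to the" (the end point being the apex). The same entry defines resorption as a loss of root length and width.

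Protocol, Data Collection Procedure and Study Groups: resorption is measured at T0, T1, T2 and T3, together with retraction, plaque and gingival health. The Data Collection Procedure classes resorption as a radiographic measurement and the other three as clinical ones.

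Protocol, Material & Methods: the design is open-label and split-mouth.

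Protocol, Randomization and Allocation Sequence Concealment: two roles are tied to the allocation sequence. Of the block randomization, the protocol says "This will be controlled by a research faculty member of the Section of Dentistry at AKUH". Of the envelopes, it says that they are opened "according to the ascending order sequence already generated by the principal investigator who is also a biostatistician".

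**The concern.** The open-label label covers two different situations. At the chair, the assessor sees the spring or chain while measuring, and masking is not practical. A periapical film can be set aside, stripped of its labels and read later. The protocol applies the same unblinded rule to both and gives no reason for extending it to films.

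Locating cusp tip and apex on a film involves judgement. If the reader knows which device the tooth carried and at which visit the film was taken, an expectation about one device can affect follow-up readings more on that side than on the other. Each patient supplies a direct contrast between devices, so a tendency of this kind enters the resorption comparison. Recruiting more patients does not remove it.

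Resorption is named first in the secondary objective, and the Rationale gives the scarcity of comparative evidence on it as a reason for the trial.

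**Working it through.** **1. Is the film reading covered by the unblinded rule?** The Blinding section names assessors without exception. Data Collection Procedure and Study Groups place resorption among the measurements at all four visits. Operational Definitions make it a length on a film. So yes. The protocol does not say outright who reads the films. It says that the co-investigator records all measurements, and it mentions assessors separately. Either way, the reader is declared unblinded.

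**2. What kind of reading error does harm?** Take resorption as the fall in read length from T0 to T3, in line with the definition as a decrease. Let s(device, visit) be the reader's systematic shift. The bias in the spring-minus-chain difference is

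B = [s(spring, T0) − s(spring, T3)] − [s(chain, T0) − s(chain, T3)].

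- Shift depends on device only, for example −0.1 mm on every spring film: B = [−0.1 − (−0.1)] − [0 − 0] = 0.
- Shift depends on visit only, for example −0.1 mm on every T3 film: B = [0 − (−0.1)] − [0 − (−0.1)] = 0.
- Shift depends on both, for example −0.1 mm on spring films at T3 only: B = [0 − (−0.1)] − [0 − 0] = 0.1 mm.

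The 0.1 mm is a hypothetical value to show the algebra. Only a shift that differs by device and by visit together survives, and that requires a reader who can tell both. Under this additive model, hiding the visit protects the change from T0 even where the device is not perfectly hidden.

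**3. How large could the effect be?** The protocol gives no SD for resorption, no reader error and no within-patient correlation, so this is an illustration. Inputs: 33 pairs (minimum sample size) and 46 pairs (sample after inflation). The plan's own figures reproduce: 8 × 0.68² / 0.39² × [1 + (1 − 0.39)²] = 33.4, stated as 33; 33 × 1.4 = 46.2, stated as 46. Assume one paired difference per patient, no true difference, a two-sided 5% normal test, and a net bias B of d SDs of the paired difference. The false-positive rate is

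Φ(d√n − 1.96) + Φ(−d√n − 1.96).

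| d | n = 33 | n = 46 |
|---|---|---|
| 0 | 5.0% | 5.0% |
| 0.1 | 8.9% | 10.4% |
| 0.2 | 21.0% | 27.4% |
| 0.3 | 40.7% | 53.0% |

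For d = 0.2 and n = 33: d√n = 1.149, and Φ(−0.811) + Φ(−3.109) ≈ 0.210. The rate rises with n because the bias stays fixed while the standard error shrinks.

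**4. Workload.** With four canines per patient at four visits, 46 × 4 × 4 = 736 films at most. This measures the preparation task and says nothing about the size of the bias.

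**The case against.** The trial is openly declared open-label, and it states who is unblinded. Nothing is contradicted or miscalculated, the outcome is secondary, and the bias is hypothetical. Masking may also be incomplete: the spring attaches to the canine bracket, and the measurement runs from cusp tip to apex, so the appliance lies within the measured span. The proposed reader also sees the patients. All of this stands, and it limits the weight of the point. It does not remove it, because the protocol fixes an unmasked reading where a masked one is available, and hiding the visit helps even if part of a device shows.

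Four stronger readings are tempting, and the protocol does not support them.

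- A reader might infer that masking films would protect the interim decision. That rule depends on retraction rate alone: "if the results show that the given intervention is successful in significantly improving the rate of canine retraction in patients then further trial will be" (the clause ends with recruitment being halted). Of that outcome, the protocol says "Canine retraction rate will be recorded by using a 100 mm marked scale". Masked films cannot reach it.
- A reader might infer that the analysis is declared unblinded. The Blinding sentence does not name the analysis. The inference rests on data access being limited to investigators and on the principal investigator being described as a biostatistician. Coding of sides for analysis could be settled in a statistical analysis plan that is not at hand.
- A reader might see detection bias in the fact that "The patients will be screened using the inclusion and exclusion criteria by the co-investigator". In a split-mouth design every patient receives both devices, so screening cannot favour one.
- A reader might suppose that a constant reading shift by device goes straight into the result. By step 2 of the working, it cancels in the change from T0.

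**Conclusion.** The point holds for one outcome. The protocol commits to unmasked reading of the films for root resorption, and open-label treatment does not require that. The harm comes through a reading shift that depends on device and visit together. Its size is not known from the protocol; the false-positive rates above rest on assumed values and on a paired test with one difference per patient, and do not estimate what will happen. The cancellation argument assumes that resorption is analysed as change from T0.

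Unmasked chairside measurement is a limitation of the primary outcome, and so of the interim rule, that masked film reading does not cure. This is a cheap improvement for a secondary outcome and does not undermine the primary comparison.

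**What to change.** Amend the Blinding section to state the following.

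- Periapical films are filed under a random code, cropped to one canine with the bracket band blanked, and mirrored to a common side.
- The existing co-investigator reads them in random order, without device, side or visit label.
- One named existing role that does not read films holds the code. The two statements on who generates the allocation sequence must be reconciled before that role is named.
- Chairside measurements remain open-label, and this is acknowledged as a limitation of the primary outcome and the interim rule.

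No extra reader, film or visit is needed. The cost is the protocol wording, the time to code and crop up to 736 films, and reading in batches instead of at the visit. Masking may be imperfect where part of a device stays visible, and the protocol should say so.

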Premolar extraction followed by canine retraction is one of the common practices in orthodontics to treat malocclusion such as severe crowding and proclination of anterior teeth.¹⁸ It is essential to know methods and techniques that result in minimum or no adverse effects on roots of teeth and periodontal health. This will help the clinicians to choose the best method that will result in a faster and more physiological closure of extraction spaces. Moreover, to the best of our knowledge, limited studies have compared the effects of Ni-Ti closed-coil springs and elastomeric power chains on canine root resorption, gingival health and plaque accumulation.^{8,17,22} It is necessary to establish a comparison between these methods, as it can help clinicians to provide better care and enhance the overall effectiveness of orthodontic treatment.

OBJECTIVE:

Primary Objective: The objective of this study is to compare the canine retraction rate (in mm with a 100 mm marked scale) using Ni-Ti closed-coil springs versus elastomeric power chains during canine retraction in subjects with first premolar extractions over a period of three months. **Secondary Objective:** This study will also include an assessment of canine root resorption (in mm using periapical radiograph), dental plaque accumulation and gingival health (according to indices mentioned below with CPI-TN probe) using Ni-Ti closed-coil springs versus elastomeric power chains during canine retraction in subjects with first premolar extractions over a period of three months.

HYPOTHESIS:

Null Hypothesis: There is no significant difference between Ni-Ti closed-coil spring and elastomeric power chain on the canine root resorption, retraction rate, dental plaque accumulation and gingival health in subjects with first premolar extractions.

Alternate Hypothesis: There is a significant difference between Ni-Ti closed-coil spring and elastomeric power chain on the canine root resorption, retraction rate, dental plaque accumulation and gingival health in subjects with first premolar extractions.

OPERATIONAL DEFINITIONS:

Ni-Ti Closed-coil Spring:¹⁹ (Annexure A)

Ni-Ti closed-coil spring is a passive compressed spring made up of super elastic Nickel-titanium. Two eyelets are attached to each side of the coil to facilitate its application. The eyelets will be engaged in the hooks of the second premolar and canine brackets and will apply a force of 150 gm.

Elastomeric Power Chain:²⁰ (Annexure B)

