The sample size was calculated using standard estimate where n = 8(CV2) /(PC2) [1+(1-PC)2] where PC is the proportionate change in means (PC = $(\mu 0 - \mu 1)/\mu 0$) and CV is the coefficient of variation (CV = $\sigma 0/\mu 0 = \sigma 1/\mu 1$). The study required a minimum sample size of 33 (N) patients in each group. With an inflation of 40% for an estimated loss to follow up/non-response rate, we will be including 46 (N) participants in this study, to achieve 80% power and to detect at least a 39% change in mean canine retraction rate values of 3.88 ± 2.66 mm and 5.45 ± 1.53 mm, with

elastomeric power chains and Ni-Ti closed-coil springs, respectively⁸ and 68% or less change in coefficient of variation at two-sided 5% level of significance.

SAMPLE SELECTION:

Inclusion Criteria:

- Patients aged between 13 40 years
- Patients undergoing fixed orthodontic treatment
- Patients requiring all first premolars extraction as part of orthodontic treatment
- Patients with all permanent teeth present and erupted (except for second and third molars)
- All patients who will sign the informed consent/assent form

Exclusion Criteria:

- Patients with systemic diseases that can affect tooth movements
- Patients with uncontrolled periodontal disease
- Patients with craniofacial syndromes
- Pregnant or lactating mothers
- Patients with bracket failures greater than three times per bracket during the study
- Patients on medications that can affect tooth movements
- Patients with Nickel allergy

DATA COLLECTION PROCEDURE:

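### A normality test chooses between a test of means and a rank test for retraction rate, so the quantity the trial tests can change with its data

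*Protocol*

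**What the plan says.** The Data Analysis section of the protocol states that a "Shapiro-Wilk test will be used to check the normality of the data". It does not say whether this means the values in each arm, the two arms pooled, or the within-patient differences, and it gives no level for the test. Retraction rate and the three secondary outcomes are then to be "assessed using Independent t-test for normally distributed data and Man-Whitney U test for non-normally distributed data".

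The same section says "Paired t-test will be used for the pairwise comparison", with no normality condition and without saying which comparison is meant. It also provides for an interim analysis at half the sample size, after which the trial stops if the intervention significantly improves the rate of retraction.

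The primary objective is to "compare the canine retraction rate (in mm with a 100 mm marked scale) using Ni-Ti closed-coil springs versus elastomeric power chains". It does not name a mean or a rank quantity. The Sample Size section does: it plans to detect a "39% change in mean canine retraction rate values of 3.88 ± 2.66 mm and 5.45 ± 1.53 mm". Each patient receives both devices, one on the right and one on the left of each arch.

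**The concern.** The two branches answer different questions. The t-test compares means. The Mann-Whitney test asks whether one device tends to give larger values than the other, and with skew and unequal spread it can reject when the means are equal. Under the rule as written, the trial's own outcome data decide which question is answered. The answer can differ between outcomes, between visits, and between the look that may stop the trial and the final analysis.

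The planning figures make the rank branch a live possibility. Distance moved can hardly be negative, yet 3.88 mm with an SD of 2.66 mm leaves little room above zero, and the two planning SDs differ by a factor of 2.66/1.53 = 1.7. At stake is whether a significant primary result can be read as faster mean retraction, which is what the trial is sized to show.

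**Working it through.** **Inputs from the protocol.** Means and SDs are 3.88 (2.66) mm for chains and 5.45 (1.53) mm for springs. The level is two-sided 5% and power is 80%. The sample size is 33 per group, with 46 enrolled to allow for loss. The formula assumes a common coefficient of variation (CV).

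**Assumptions, because the protocol gives no value.** These are the shape of the distribution, the left-right correlation within a patient, Shapiro-Wilk at 5% in each arm, and one pair of values per patient. Dividing distance by a fixed three months changes neither the shape nor any test result.

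1. *The plan's own figure.* With CV 0.68 and proportionate change 0.39 as stated, 8 × 0.68² / 0.39² × (1 + 0.61²) = 33.4, which agrees with 33. Then 33 × 1.4 = 46.2, which agrees with 46. This is a calculation for means.

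2. *Is a normal shape plausible?* A normal curve with these chain values puts Φ(−3.88/2.66) = Φ(−1.46) = 7.2% of distances below zero. That argues against normality but does not identify the true shape.

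3. *How often is the rank test chosen?* The table shows simulations at the planning means and SDs, n=33, with Mann-Whitney used if either arm fails Shapiro-Wilk.

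| Assumed shape | Rank test chosen |
|---|---|
| Normal | 9% |
| Zero-truncated normal | 54% |
| Beta (bounded at 9 to 12 mm) | 54-66% |
| Weibull | 70% |
| Gamma | 82% |
| Lognormal | 93% |

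If the arms are pooled before testing, the non-normal shapes give 19-61%.

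4. *Interim against final.* With a gamma shape, the planned effect and correlation 0.3, the rank test is chosen in about 63% of trials at n=23 (half of 46) and about 81% at n=33. The two looks can therefore rest on different tests.

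5. *Error of the whole rule when the means are equal* (both 3.88 mm, SDs 2.66 and 1.53, n=33). At correlation 0 it is 7.0-15.1% over the non-negative shapes. In the gamma case the medians differ by about 0.4 mm in favour of springs although the means are equal, which is why the rank test rejects too often. Gamma results by correlation are below; ranges cover separate simulation runs.

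| Correlation | Rule, SDs 2.66 and 1.53 | Rule, identical distributions |
|---|---|---|
| 0 | 12-13% | about 5-6% |
| 0.3 | 8-10% | 2-3% |
| 0.5 | 6-8% (most runs near 6%) | 1% |
| 0.7 | 4-5% | near 0% |

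A paired t-test gave 4.5-5.7% across these gamma cases. At correlation 0.5 it gave 4.4-6.4% over all the shapes run.

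6. *Why correlation matters.* Both branches ignore the pairing, which makes them conservative when the sides are positively correlated and offsets the excess from unequal spread. At correlation 0.5 (gamma, unequal SDs) the independent t-test rejects in about 1.5% of trials and the Mann-Whitney test in about 6-8%. The pre-test thus switches between two tests with very different error rates.

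**The case against.** The strongest reply is that the protocol gives means and SDs but no shape, so nothing in it shows that the rank test would be chosen. This stands as far as frequency goes: the share runs from 9% to 93% depending on the shape, and it is often below half if the arms are pooled. A reader might infer that the planning figures alone send the primary outcome to the rank test in most trials. They do not.

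A second reply is that the excess error needs equal means, unequal SDs and weak correlation together. This also stands. The Hypothesis section states only that the devices do not differ; if the two distributions are identical, the rule does not exceed about 5-6%. Under the common CV assumed by the sample-size formula, equal means imply equal SDs, and Mann-Whitney then rejects in 4.3-5.8% of trials at n=33. Against this, the protocol's own figures give CVs of 2.66/3.88 = 0.69 and 1.53/5.45 = 0.28, so they contradict that assumption. A split-mouth design also aims at high correlation, and at 0.7 the excess has gone.

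Third, a reader might assume that normality is checked on raw values; the text leaves this open. The unconditional paired t-test might be meant for the device comparison, but the protocol does not say so, and the sentence on comparing the two groups names independent tests.

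Finally, this is not a detail left to a statistical analysis plan. The protocol states the selection rule and applies it to the primary outcome.

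**Conclusion.** The point holds in a conditional form. It is certain from the text that a normality test on unspecified data chooses between a test of means and a rank test for the primary outcome, in a split-mouth trial sized on means.

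The size of the harm is not certain. At n=33, the number the plan expects after loss, the error for equal means can reach about 7-15% if distances are skewed, SDs differ as planned, each arm is tested and the sides are uncorrelated. For a gamma shape it is about 6% at correlation 0.5 and 4-5% at 0.7. With identical distributions it is about 5% at correlation 0 and far lower otherwise. The flat statement that the rule fails to hold 5% is therefore too strong. What can be said is that its error may lie above or below 5%, depending on features the protocol does not fix, while a paired t-test stays near 5% in every case examined.

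Using independent tests on paired data is the larger related fault, and the same change corrects it.

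**What to change.** In the Data Analysis section, remove the Shapiro-Wilk selection rule for the device comparison of retraction rate. State that the primary analysis, at both the interim and the final look, is the mean within-patient spring-minus-chain difference with its 95% confidence interval, by a paired t-test or an equivalent mixed model. State also how the two arches of a patient are combined, for example by averaging them before taking the difference. Report a signed-rank or bootstrap result as a sensitivity analysis, whatever a normality test shows.

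The text change is about two sentences. The statistical cost is lower nominal power if the data are skewed. For a gamma shape at the planned effect and n=33, the paired t-test gives about 79% against 93% for the two-stage rule at correlation 0, and about 93% against 96% at 0.5. Part of that gap arises because the rank test in this setting rejects too often when the means are equal. Even at correlation 0, the paired test is close to the 80% planned.
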